7.1 Demographics and Other Baseline Characteristics

Descriptive statistics of demographics and other relevant baseline characteristics will be presented for all subjects in the mITT and PP analysis sets by treatment group unless specified otherwise. In addition, they will be summarized by investigational site and by region (US or non-US) for the mITT analysis set.

Categorical data will be summarized using numbers and percentages. The percentages are based on the total number of subjects with a corresponding assessment. Continuous data will be presented using the number of subjects, mean, standard deviation, median, inter-quartile range, minimum and maximum.

All demographics and baseline data will be listed and sorted by investigational site and subject ID.

No missing data will be imputed unless specified otherwise.

7.1.1 Demographics

The following demographic information will be tabulated: age at randomization (years), age at randomization (<65 years, or \geq 65 years), sex, ethnicity (Hispanic or Latino, Not Hispanic or Latino), race (American Indian or Alaska Native, Asian, Black or African American, Native Hawaiian or Other Pacific Islander, White) and country (US, non-US).

7.1.2 Body Measurements

The following baseline body measurements made at screening will be summarized: body weight (kg), height (m), and BMI (kg/m^2). In addition, frequency tables for BMI (<20, 20 - <25, 25 - <30, 30 - <35, 35 - <40, 40 - <45, or \geq 45 kg/m^2) will be produced.

7.1.3 Comorbidity

The following comorbidities that warrant the use of supplemental graft material will be recorded at the screening visit:

- Radiographic evidence of bone defect, deficit, subsidence or subchondral cyst
- More than one joint to be fused
- Involvement of other adjacent or nonadjacent joints
- Large surface area
- Intra-articular or extra-articular deformity
- Post-traumatic arthritis
- Diagnosis of osteoporosis

The prevalence of each comorbidity (yes, no) will be tabulated. A separate table will summarize the number of comorbidities per subject both as the actual number (i.e., 1 to 7) and in a cumulative manner (i.e., at least 1, at least 2, ..., and at least 7).

7.1.4 History and Physical Examination of Ankle/Hindfoot

The affected side of ankle/hindfoot will be determined by the planned fusion side. If a subject indicates that the contralateral foot or ankle is also affected by the same condition, the affected side will be considered bilateral. The affected side (right, left, or bilateral), the primary etiology of the condition that required fusion (primary osteoarthritis, post-traumatic arthritis, or other), and the alignment of ankle/hindfoot (normal, pes plano valgus, cavovarus/equinovarus, hindfoot varus, or hindfoot valgus) will be summarized.

7.1.5 Surgical Site and Non-union Risk Factors

The following definitions of planned surgical site and non-union risk factors will be used for the stratified randomization:

- Planned surgical site: tibiotalar (ankle) or any of talocalcaneal, calcaneocuboid, or talonavicular joints (hindfoot)
- Obesity: $\text{BMI} \geq 30 \text{ kg/m}^2$
- Diabetes: History of Type 1 or Type 2 diabetes mellitus
- Previous hindfoot/ankle surgery: Previous surgery on the target hindfoot/ankle
- Smoking history: Any smoking history prior to screening

The randomization strata, that is, planned surgical site and presence or absence of any of obesity, diabetes, previous hindfoot/ankle surgery, or smoking history will be tabulated. The prevalence of each non-union risk factor and planned surgical site will also be tabulated.

7.1.6 Other Baseline Characteristics

Baseline weight-bearing pain, FAAM-ADL score, SF-12 physical component summary (PCS), and SF-12 mental component summary (MCS) will be summarized.

7.2 Medical History

Medical history will be coded for the system organ class (SOC) and preferred term (PT) using the Medical Dictionary for Regulatory Activities (MedDRA) version effective at trial start or later. The version of the MedDRA used for the final analyses will be documented. Medical history will be summarized by the SOC (in alphabetical order) and PT (in decreasing order of frequency) for the mITT analysis set.

Medical history will be listed by investigational site and subject ID.

7.3 Prior and Concomitant Medication

All medications will be coded using the World Health Organization Drug Reference List and categorized as either prior or concomitant medications.

- 1) Prior medication; i.e. medication taken exclusively prior to treatment (i.e. with stop date before date of the surgery)
- 2) Concomitant medication, i.e. medication taken during the treatment period (i.e. medication that was not stopped before date of the surgery and not started after the end-of-trial visit)

If the timing of the dose of a medication cannot be established in relation to the date of the surgery, it will be considered as concomitant medication.

Prior and concomitant medications will be summarized by the Anatomical Therapeutic Chemical (ATC) classification 1st level (alphabetically) and ATC classification 2nd level (in decreasing order of frequency) for the mITT analysis set.

Prior and concomitant medications will be listed by investigational site and subject ID.

7.4 Perioperative Characteristics

Perioperative characteristics of the index procedure will be summarized by treatment group for the mITT analysis set. In addition, they will also be summarized by investigational site and by region (US or non-US) for the mITT analysis set. Perioperative characteristics will be listed by investigational site and subject ID.

7.4.1 Procedure

The length of the procedure, length of the hospital admission, treated side, treated joint(s), type of surgical incision, estimated blood loss at fusion site, estimated blood loss at harvest site, and blood transfusion (yes/no) will be summarized.

The length of the procedure will be calculated as the time between the first incision and skin closure. Treated joint(s) will be tabulated for ankle or any of the hindfoot joints with breakdown of all combinations of treated hindfoot joints.

7.4.2 Hardware

Number of screws used as the primary fixation per joint will be summarized for each joint as well as each type of fusion (i.e., joint(s) treated).

7.4.3 Medications

Perioperative medications will be summarized by the ATC classification 1st level (alphabetically), ATC classification 2nd level (in decreasing order of frequency). In addition, the type and length of anesthesia will be summarized.

The lengths of anesthesia will be calculated from the earliest start time and the latest end time of any type of anesthesia.

8 Exposure and Treatment Compliance

8.1.1 Extent of Exposure

The amount of graft material used will be summarized as a continuous variable in cm^3 as well as a categorical variable ($0 < - \leq 5 \text{ cm}^3$, $5 < - \leq 10 \text{ cm}^3$, or $> 10 \text{ cm}^3$) by treatment group for the mITT analysis set in following manners:

- Total amount used
- Total amount used for each joint
- Total amount used for each combination of joint(s) treated
- Total amount used for procedures involving single, double, and triple hindfoot joints, respectively

For the ABG group, the harvest site, harvest side, type of incision at the harvest site, and volume harvested will be summarized.

The length of the follow-up from the day of the surgery will be summarized together with the following categorical summaries:

- $< 2 \text{ weeks}$, $2 - < 4 \text{ weeks}$, $4 - < 12 \text{ weeks}$, $12 - < 24 \text{ weeks}$, $24 - < 36 \text{ weeks}$, $36 - < 52 \text{ weeks}$, $52 - < 64 \text{ weeks}$, $64 - < 78 \text{ weeks}$, and 78 weeks or more
- At least 1 day, at least 2 weeks, at least 4 weeks, at least 12 weeks, at least 24 weeks, at least 36 weeks, at least 52 weeks, at least 64 weeks, and at least 78 weeks

8.1.2 Treatment Compliance

The investigator-reported response for the compliance to the protocol-defined procedure requirements and the instructions for use (if applicable) will be summarized by treatment group for the mITT analysis set.

9 Efficacy

9.1 General Considerations

Non-inferiority tests will be conducted at a one-sided 5% significance level whereas superiority tests will be conducted at a two-sided 5% significance level per an agreement with the FDA in the AMPLEX IDE.

All efficacy analyses will be conducted for the mITT analysis set unless specified otherwise. The primary and key secondary efficacy endpoints will be analyzed by a fixed-sequence procedure according to the following order to maintain the overall Type 1 error rate to a one-sided 5% for non-inferiority and a two-sided 5% for superiority testing.

- 1) Non-inferiority of AMPLEX to ABG in the primary efficacy endpoint (primary analysis)
- 2) Non-inferiority of AMPLEX to ABG in the key secondary efficacy endpoint
- 3) Superiority of AMPLEX to ABG in the key secondary efficacy endpoint
- 4) Superiority of AMPLEX to ABG in the primary efficacy endpoint

Testing procedure will begin with the non-inferiority test for the primary efficacy endpoint, and each test will be conducted without adjustment of multiplicity as long as all preceding tests are significant. All other secondary endpoints will be presented with the point estimate of the treatment group difference and the corresponding 2-sided 90% and 95% confidence intervals.

For visit-based data, the data collected on the day that is closest to the scheduled trial day within a window specified in Table 1 will be assigned to the corresponding analysis visit. If the closest day cannot be uniquely identified for an analysis visit, the data collected on an earlier trial day will be assigned to the analysis visit. Visit windows for the analysis are specified in a way to utilize all collected data as much as possible and are different from the protocol specified visit windows.

Table 1 Scheduled trial day and window for analysis visits

Analysis visit	Scheduled trial day	Analysis window
Baseline	Day -84 to Day 1	Up to prior to the initiation of surgery
Post-Operative CT and X-ray	Day 1	Day 1 to Day 29
Week 2	Day 15	Day 2 to Day 29
Week 6	Day 43	Day 30 to Day 64
Week 12	Day 85	Day 65 to Day 127
Week 24	Day 169	Day 128 to Day 267
Week 52	Day 365	Day 268 to Day 456
Week 78	Day 547	Day 457 to Day 637

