## **4.2 Method of Assigning Subjects to Treatment Groups**

### **4.2.1 Recruitment**

Each Investigator will recruit subjects who are undergoing surgical treatment for hindfoot or ankle arthritis equitably in an effort to ensure to the best extent possible that the subject pool is representative in gender, race, ethnicity, and age of the population affected by the condition being studied. The Investigator or his/her designee such as the study coordinator will notify Ferring or their designee of each potential subject. The coordinator will assign each consented subject a subject identification number in consecutive, ascending, and chronological order. This number will serve as a subject's identifier on all study-related documentation.

All subjects screened for the trial will be recorded on a screening log, including subject age, sex, race and ethnicity. The reason of non-eligibility for all subjects who are deemed ineligible by the Investigator should also be recorded on the study screening log. The screening log serves as a method for Ferring or their authorized designee to ensure that there is no selection bias in the trial. Screening logs will be periodically examined to evaluate reasons for non-enrollment of women or other key demographic groups.

Once it is determined that the subject is eligible for the study, the site will inform the Ferring representative or designee of the surgery date. The subject will be randomized according to the randomization schedule for each site as close to the time of surgery as possible, with the recommendation that the randomization be performed on the day of the surgical procedure. The subject randomization number will then be recorded on the relevant CRF. The randomization number will be assigned prior to surgery in a sequential, chronological order. Randomization numbers will not be reassigned.

Evaluations performed at each study visit are summarized in Section 6: Trial Procedures. If a subject misses a visit, all reasonable efforts should be made to reschedule the missed visit within the allocated visit window. If the visit cannot be rescheduled within the allocated visit window, the site should schedule a visit with the subject as soon as possible.

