##### **7.2.2.2 Weight-bearing Pain VAS**

Weight-bearing pain at fusion site will be assessed using a VAS. Subjects will mark the location on a 100-millimeter line corresponding to the amount of pain they experienced with 0 mm being “no pain” and 100 mm being “the worst pain imaginable”. The weight-bearing pain VAS will be completed at screening and at 12, 24 and 52 weeks post procedure. The assessment and its instructions for use will be provided in the SRM.

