9.2 Primary Endpoint

9.2.1 Primary Variable Analysis

The primary efficacy endpoint will be the proportion of subjects who meet all of the following criteria for the SPC at 52 weeks:

- Improvement in pain on weight-bearing at fusion site (≥ 20 mm reduction from baseline on 100 mm VAS)
- Absence of significant graft harvest site pain (< 20 mm on 100 mm VAS)
- Improvement in Foot and Ankle Ability Measure Activities of Daily Living subscale (FAAM-ADL) (≥ 8 points improvement from baseline)
- Absence of device related or procedure related SAEs (up to Week 52)
- Absence of secondary surgical or nonsurgical interventions intended to promote fusion (up to Week 52)

The primary analysis will assess a non-inferiority of AMPLEX to ABG, and it will be claimed if the lower bound of the 2-sided 90% CI for the difference of the proportions (AMPLEX minus ABG) is greater than -12.0%. The superiority will be claimed if the lower limit of the 2-sided 95% CI is greater than zero. The CI will be constructed with the normal approximation to the binomial. In addition, the response status for each component will be summarized.

A subject will be considered an SPC success if he/she meets all of the SPC criteria, otherwise, the subject will be considered an SPC failure. The SPC response status will be determined for 12, 24, and 52 weeks. The response status for the visit-based components (i.e., weight-bearing pain, graft harvest site pain, and FAAM-ADL) will be assessed for each time point based on the windowed analysis visits. The response status for the non-visit-based components (i.e., absence of device or procedure related SAEs and secondary interventions to promote fusion) will be assessed in a period up to the actual visit date that the corresponding visit-based variables for a particular analysis visit are collected. If the actual visit dates among the visit-based variables are different at the analysis visit, the latest visit date among them will be used to determine the period for the assessment of the non-visit-based variables. If any of the components of the SPC at an analysis visit is missing, the SPC response status will be considered missing for the analysis visit. Note that the graft harvest site pain will be collected only for the ABG group, and therefore, no data for this component will be recorded for the AMPLEX group.

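### SAP Table 1 assigns a Week-52 pain, FAAM-ADL, harvest-site or CT value taken after Day 456 to a Week-78 visit where these endpoints are not derived (minor, cheap to fix)

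*SAP*

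**What the plan says.** **Assignment.** SAP 9.1 goes by the day on which data were collected, not by the nominal visit: "the data collected on the day that is closest to the scheduled trial day within a window specified in Table 1 will be assigned" to that analysis visit. The Week-52 row of Table 1 reads "Day 268 to Day 456" and the Week-78 row "Day 457 to Day 637". No variable is exempt. The stated purpose is: "Visit windows for the analysis are specified in a way to utilize all collected data as much as possible".

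**What is measured when.** Protocol 7.2.2.2: "The weight-bearing pain VAS will be completed at screening and at 12, 24 and 52 weeks post procedure". Protocol 7.2.2.1 (FAAM-ADL), 7.2.2.4 (harvest-site pain) and 7.2.1.2 (CT) also stop at 52 weeks. Protocol 6.1.11 lists none of the four at the 78-week visit.

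**Late visits.** Protocol 4.2.1: "If the visit cannot be rescheduled within the allocated visit window, the site should schedule a visit with the subject as soon as possible". It gives no latest day.

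**Derivation.** SAP 9.2.1: "The SPC response status will be determined for 12, 24, and 52 weeks". SAP 9.3.1 does the same for CT fusion. Both use the windowed visits, and one missing component makes the status missing. A missing Week-52 status takes the last available status, or failure if there is none.

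**The concern.** A mid-point split is sensible where two scheduled assessments of the same variable compete for the days between them. For these four variables nothing competes after Week 52. The split serves no purpose for them, and it can turn an observed outcome into a missing one.

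The replacement is the Week-24 status, the Week-12 status if Week 24 is also missing, or failure. No planned analysis uses the observed value. Missing-equals-failure counts the subject as a failure, multiple imputation draws the Week-52 components from earlier visits, and the tipping-point analysis treats the outcome as unknown. The ITT, per-protocol and as-treated analyses repeat the primary method. The repeated-measures models in SAP 9.3.2 also lose the Week-52 pain and FAAM-ADL values.

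At stake is a little avoidable missing data in the primary and key secondary non-inferiority tests. Equal lateness by arm cannot be presumed. Subjects and investigators know the treatment after surgery (Protocol 3.4.3), and an ABG subject needs three visit-based components where an AMPLEX subject needs two (SAP 9.2.1).

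**Working it through.** **1. Table 1 boundaries.** The scheduled days are 15, 43, 85, 169, 365 and 547. The mid-points are 29, 64, 127, (169+365)/2 = 267 and (365+547)/2 = 456. The last limit is 547+90 = 637. All match Table 1, so it is a mid-point split throughout.

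**2. How late a visit must be.** The protocol window for Week 52 is 365 ± 30, that is Day 335 to 395. Day 457 is 457−365 = 92 days after the target and 457−395 = 62 days after that window closes. The protocol window for Week 78 opens on Day 547−30 = 517. The gap is therefore mainly Day 457 to 516, which is 60 days.

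**3. The plan's power.** Inputs from SAP 3.2: ABG 60%, AMPLEX 62%, margin 12 points, one-sided 5%.

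SE = √[p_C(1−p_C)/n_C + p_T(1−p_T)/n_T]; power = Φ((p_T − p_C + 0.12)/SE − 1.645).

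- 132/264: SE = √(0.24/132 + 0.2356/264) = 0.0521; 0.14/0.0521 − 1.645 = 1.04; power 85.2%. The plan's 85% with 396 subjects is reproduced.
- 160/320: SE = 0.0473; power 90.6%. This is the base case below, because carrying a status forward or scoring failure keeps these subjects in the analysis.

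**4. Effect of replacement.** The documents give neither the share of late visits (L) nor the success rate of the replaced status (q), so both are assumptions. Each arm's rate becomes p(1−L) + qL. I take the same q in both arms and assume that late subjects would otherwise succeed at the planning rate.

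Equal lateness: the q terms cancel and the difference is 2.0 × (1−L) points.

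- L = 1% (4.8 of 480): 1.98 points
- L = 5% (24 of 480): 1.90 points

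The shift is 0.02 to 0.10 points. Over q from 0% to 60%, power at L = 5% is 89.6% to 90.2%.

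Unequal lateness:

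| Late share | q = 60% | q = 40% | q = 0% (all scored failure) |
|---|---|---|---|
| AMPLEX 5%, ABG 0% | +1.9 (90.2%) | +0.9 (86.0%) | −1.1 (74.2%) |
| AMPLEX 0%, ABG 5% | +2.0 (90.6%) | +3.0 (93.6%) | +5.0 (97.3%) |

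Each cell gives the difference in points and the power at 320/160. Example: 0.62 × 0.95 + 0.40 × 0.05 = 0.609, and 0.609 − 0.600 = +0.9 points. The q = 0% column is an extreme, since it needs every late subject to lack any earlier status or to have failed earlier.

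**5. How far the window can sensibly run.** A Week-24 value on Day 169 is 196 days from Day 365. A late value is further away than that once it passes Day 365+196 = 561. Day 637 is 272 days away. Day 516 is 516−365 = 151 days away, against 365−199 = 166 days for the latest Week-24 value inside its protocol window (Day 139 to 199). The Week-24 analysis window is wider and runs to Day 267, so a Week-24 value taken after Day 214 (365−151) would be nearer to Day 365 than one on Day 516.

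**The case against.** A 52-week endpoint needs a cut-off somewhere. Table 1 already accepts values 61 days past the protocol window (456−395), and its stated aim is qualified by what is possible. The affected visits must be very late although sites are told to act promptly. The tipping-point grid covers every combination of outcomes for subjects with missing status, so the late subjects' true outcomes lie somewhere on it.

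Much of this stands. A cut-off is legitimate and the exposure is narrow. What does not stand is the choice of Day 456 for variables with no later assessment: there the mid-point protects nothing. The grid contains the right answer but does not mark it, so it does not replace the use of a known value.

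A reader might infer more than the documents support:

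- **That observed outcomes are thrown away.** They stay in the database. They are only unused in the Week-52 derivations, and only when no other value of that variable falls in Days 268 to 456.
- **That the window should run to Day 637, or that missed questionnaires should be completed at Week 78.** Values after Day 561 are further from Day 365 than a Day-169 value. A Week-78 value on schedule is 547−365 = 182 days late, and one on Day 577 is 212 days late. The look-back for SAEs and interventions runs to the actual visit date (SAP 9.2.1), so a longer window would also give late subjects more time to fail.
- **That SF-12 belongs in the list.** The synopsis schedule marks it at Weeks 52 and 78, whereas Protocol Table 3 and SAP Appendix 3 mark Weeks 24 and 52. That must be reconciled first.

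**Conclusion.** The point holds as a minor defect. For weight-bearing VAS, FAAM-ADL, harvest-site VAS and CT, Table 1 can replace an observed late Week-52 outcome with an earlier status or failure, against its own stated aim.

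With assumed equal lateness of 1% to 5% per arm, the difference moves by 0.1 point or less against a 12-point margin. A larger shift needs lateness that differs by arm: about 0.1 to 1.1 points toward inferiority if 5% of AMPLEX and no ABG subjects are late and 60% to 40% of them carry a success forward. The documents give no late-visit rate and no evidence of such a difference, so they do not support a claim that the non-inferiority conclusion is at risk. The case for change is that the repair is cheap and puts observed outcomes in place of imputed ones.

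**What to change.** Add a footnote to SAP Table 1 before database lock:

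- For weight-bearing VAS, FAAM-ADL, harvest-site VAS and CT, the Week-52 window runs from Day 268 to Day 516, the day before the Week-78 protocol window opens. The value closest to Day 365 is still taken.
- For a value after Day 456, the look-back for related SAEs and for interventions to promote fusion ends at Day 456, so that late subjects get no longer failure period than now.
- The footnote should also say what happens if such an intervention falls after Day 456 but before the late value. The intervention would not count as a failure, yet it could influence that value.

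Do not extend to Day 637, do not collect missed questionnaires at Week 78 as Week-52 data, and leave SF-12 out until its schedules agree.

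The cost is one footnote and minor programming. A few Week-52 values will be up to 151 days late. Subjects with a value in Days 268 to 456 keep it, with one rare exception: a value on Day 268 to 272 (97 to 93 days early) can lose to a second one on Day 457 to 461 (92 to 96 days late). If the team prefers to keep Table 1 as it is, the alternative is a sensitivity analysis for both endpoints that uses the late observed values.
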